## **5.2 Withdrawal from the Study, Discontinuation of Study Product, or Study Termination**

### **5.2.1 Withdrawal from the Study or Discontinuation of the Study Product**

Subjects may voluntarily withdraw their consent for study participation at any time without penalty or loss of benefits to which they are otherwise entitled.

An investigator may also withdraw a subject from receiving the study product for any reason. Follow-up safety evaluations will be conducted, if the subject agrees. If a subject withdraws or is withdrawn prior to completion of the study, the reason for this decision must be recorded in the case report forms (CRFs). If a subject withdraws from the study, he/she may request destruction of any samples taken, and the Investigator must document this in the site study records and communicate this request to the Sponsor. However, the investigator will inform the subject that already collected data will be retained and analyzed even if the subject withdraws from this study.

The reasons for withdrawal might include, but are not limited to the following:

- Subject withdraws consent;
- subject becomes noncompliant;
- medical disease or condition, or new clinical finding(s) for which continued participation, in the opinion of the investigator might compromise the safety of the subject, interfere with the subject's successful completion of this study, or interfere with the evaluation of responses;
- subject lost to follow-up;
- request of primary care provider;
- at the request of the IRB/IEC, FDA, or NIAID;
- the subject's well-being, based on the opinion of the investigator.

---

The investigator will inform the subject that already collected data will be retained and analyzed even if the subject withdraws from this study. Subjects will be informed that they have the right to withdraw from the study at any time for any reason without prejudice to their medical care. If the subject has received the study drug, data collected for withdrawn subjects will be evaluated for safety and PK.

In all cases of withdrawal, the reason for withdrawal will be recorded. Subjects who receive any amount of study product and who are discontinued from the study will be asked to complete all Day 21 safety assessments including follow-up of any AEs prior to termination from the study.

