## 10.5 Final Analysis Plan

The safety analysis population will include all subjects that received any amount of study product and will be analyzed by treatment received. Placebo subjects may be pooled across multiple cohorts for analysis. The PK analysis population will include all subjects with at least one measurable PK concentration.

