6.3.2.1. PK Analysis Subset

The PK Analysis Subset will be based on the PK Analysis Population and will include all subjects who completed the PK part of the trial in each dosing period without any protocol deviation that would likely affect the PK results and who have an evaluable plasma or urine concentration for either VT-1598 or VT-11134 from which at least a subset of the designated PK parameters can be determined. The order that reasons will be considered for a PK Analysis Subset will be: excluded from the PK Analysis Population, occurrence of protocol deviation(s) with potential to impact PK, PK data is insufficient to estimate any plasma or urine PK parameters.

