10. PHARMACOKINETICS

10.1. Graphical and Tabular Summaries of Pharmacokinetic Profiles

The PK Analysis Subset will be used when summarizing plasma and urine PK concentrations. For both measured analytes in each specimen type, concentrations below the limit of quantification (BQL) collected before the first measurable PK concentration above the lower limit of quantification (LLOQ) will be treated as 0 for plotting and for all calculations including noncompartmental analysis (NCA) and concentration summary statistics. All other BQL values, for each analyte within each specimen type, observed after the first measurable concentration will be treated as missing. There will be no imputation of missing concentrations. The geometric mean (GM) of concentrations will be treated as missing for sets of data points containing a BQL value.

Collection of plasma or urine samples outside of the protocol defined time window for the timepoint will not result in exclusion of the sample result from NCA. Plasma or urine samples collected out of window will be evaluated on a case by case basis. Results from PK plasma samples that were collected substantially outside of the protocol defined time window will be excluded from concentration summary statistics by nominal timepoints and plots of mean concentration by nominal timepoint. Substantially out-of-window samples are defined to be twice the size of the protocol required windows: \pm 10 minutes of the nominal timepoint for the 0.5 h post dose sample; \pm 20 minutes of the nominal timepoint for the remaining post dose samples on Day 1; \pm 1 hour of the nominal timepoint for the remaining inpatient days, Day 2, Day 3, and Day 4; \pm 2 days for the follow-up visits, Day 7 and Day 14; and \pm 4 days for the final study visit, Day 21.

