10.3. Statistical Analysis

The PK Analysis Subset will be used for statistical analyses of plasma and urine PK parameters described above.

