Analysis Populations	Reason Subjects Excluded	40 mg Fasted (N=X)	80 mg Fasted (N=X)	160 mg Fasted (N=X)	160 mg Fed (N=X)	320 mg Fasted (N=X)	640 mg Fasted (N=X)	Placebo (N=X)	All Subjects (N=X)
		n (%)	n (%)	n (%)	n (%)	n (%)	n (%)	n (%)	n (%)
Safety Population	No study product received	x (x)	x (x)	x (x)	x (x)	x (x)	x (x)	x (x)	x (x)
PK Analysis Population	Any reason	x (x)	x (x)	x (x)	x (x)	x (x)	x (x)	x (x)	x (x)
	Subject received placebo	x (x)	x (x)	x (x)	x (x)	x (x)	x (x)	x (x)	x (x)
	Assigned dose not received or completed	x (x)	x (x)	x (x)	x (x)	x (x)	x (x)	x (x)	x (x)
	Subject has no measurable concentration in plasma or urine at any timepoint	x (x)	x (x)	x (x)	x (x)	x (x)	x (x)	x (x)	x (x)
PK Analysis Subset	Any reason	x (x)	x (x)	x (x)	x (x)	x (x)	x (x)	x (x)	x (x)
	Excluded from PK Analysis Population	x (x)	x (x)	x (x)	x (x)	x (x)	x (x)	x (x)	x (x)
	Protocol deviation(s) with potential to impact PK	x (x)	x (x)	x (x)	x (x)	x (x)	x (x)	x (x)	x (x)
	PK data insufficient to estimate any PK parameters	x (x)	x (x)	x (x)	x (x)	x (x)	x (x)	x (x)	x (x)

Notes: N=Number of subjects enrolled/randomized.

Results from subjects in Cohort 3 that continued on to Cohort 6 are summarized separately for each dosing period in the All Subjects and Placebo columns.

Table 11: Ineligibility Summary of Screen Failures

[Implementation Note: Although subjects may meet multiple criteria for exclusion, each subject will only be counted under one reason for exclusion in this table. The final summary table will include only inclusion/exclusion criterion with at least 1 subject. Criteria that were not met by any subjects will be excluded from final table. If any of the criteria footnotes change in subsequent versions of the study protocol, the updated text should be used instead.]

Inclusion/Exclusion Category	Inclusion/Exclusion Criterion	Subjects Excluded	
		n ^a	% ^b
Inclusion and Exclusion	Number of subjects failing any eligibility criterion	x	100
Inclusion	Any inclusion criterion	x	xx
	Willing and able to provide written informed consent and authorization for use of protected health information	x	xx
	Willing and able to comply with protocol requirements, instructions, and protocol-stated restrictions (including confinement to the CRU) and is likely to complete the study as planned	x	xx
	Male and female subjects, 18-45 years of age (inclusive)	x	xx
	Subject is in good health to be safely enrolled in this protocol and determined by medical history and physical exam		

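### The completion condition in SAP 6.3.2.1, read literally, drops a withdrawn subject's observed Cmax and Tmax from the concentration summaries and the Section 10.3 tests, and it conflicts with the SAP's own exclusion reasons

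*SAP*

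**What the plan says.** SAP 6.3.2.1 builds the PK Analysis Subset from the PK Analysis Population. The Subset "will include all subjects who completed the PK part of the trial in each dosing period", without a deviation likely to affect PK, and with concentrations "from which at least a subset of the designated PK parameters can be determined". What counts as completing the PK part is not defined. The ordered reasons for exclusion from the Subset then read "excluded from the PK Analysis Population, occurrence of protocol deviation(s) with potential to impact PK, PK data is insufficient to estimate" any plasma or urine parameter. Table 10 has rows for the same three reasons, the last being "PK data insufficient to estimate any PK parameters". Neither place has a reason for non-completion or withdrawal.

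The Subset is the named population in two places. SAP 10.1: "The PK Analysis Subset will be used when summarizing plasma and urine PK concentrations". SAP 10.3: "The PK Analysis Subset will be used for statistical analyses of plasma and urine PK parameters described above", which covers dose proportionality, Tmax and the fed/fasted ratios. SAP 10.2, which describes the parameter summary tables, names no population, and 6.1 permits either one. The interim analysis (6.6) uses the wider PK Analysis Population, and 6.3.2 puts all concentrations in listings.

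The protocol sets no completion condition. Section 10.5: "The PK analysis population will include all subjects with at least one measurable PK concentration". Section 5.2.1: "If the subject has received the study drug, data collected for withdrawn subjects will be evaluated for safety and PK".

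**The concern.** Planned plasma sampling ends at 480 h (Day 21), but the early parameters are settled long before that. Protocol 9.3 presumes Cmax at 6 h, and subjects stay in the unit to 72 h. A subject who leaves after Day 4, 7 or 14 therefore has Cmax and Tmax observed and, on a literal reading, still contributes nothing to the concentration summaries or to any Section 10.3 analysis.

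Two things are at stake with six actives per group. First, withdrawal can be related to exposure, for instance when it follows an adverse event at a high dose, so the rule can remove valid data selectively. Second, the definition and the exclusion list give different answers. A programmer working from the definition drops the subject; one working from the list and Table 10 keeps the subject. The choice could then be made after the concentrations are known. Under Protocol 5.2.2 the first subject per cohort lost to follow-up after dosing is not replaced, so a group of five is a foreseeable outcome.

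**Working it through.** The plan gives no power or precision figure here (Protocol 10.2 states that none was calculated), so there is nothing to reproduce. There are three checks.

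**1. Which parameters survive withdrawal.** Inputs: sampling times from Protocol Table 2; the 6 h presumed peak from Protocol 9.3; animal half-lives of 25-33 h (rat) and 64-72 h (monkey) from Protocol 2.1, as no human value is given; and the default rules in SAP 10.2 (λz span of at least 3 half-lives, at least 3 points after Tmax, %AUCex of at most 20%). Assumed: a one-compartment oral model with k = ln 2/t½, ka chosen so that Tmax = 6 h, and concentrations still quantifiable at the last sample.

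Largest possible span = (last sample − 8 h)/t½, since 8 h is the first sample after the peak. %AUCex = ka/(ka − k) × (e^(−k·last) − e^(−ka·last)).

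| Last sample | t½ 25 h | t½ 33 h | t½ 64 h | t½ 72 h |
|---|---|---|---|---|
| 72 h: span; %AUCex | 2.56; 14% | 1.94; 23% | 1.00; 47% | 0.89; 51% |
| 144 h (Day 7) | 5.44; 2% | 4.12; 5% | 2.12; 21% | 1.89; 25% |
| 312 h (Day 14) | 12.2; 0% | 9.2; 0.1% | 4.75; 3.5% | 4.22; 5.0% |

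AUC0-inf is not reportable if the last sample is at 72 h or earlier. It is reportable from 144 h at 25-33 h half-lives, and only from 312 h at 64-72 h. Cmax and Tmax are observed in every row.

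**2. Precision if the loss is unrelated to exposure.**

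- Fed/fasted ratio, groups treated as independent (SAP Section 15 reports that only one subject returned). The 90% CI half-width on the log scale, in SD units, is t(0.95, n1+n2−2) × √(1/n1 + 1/n2). For 6 v 6: 1.812 × 0.577 = 1.046. For 5 v 6: 1.833 × 0.606 = 1.110. Ratio 1.110/1.046 = 1.06, so about 6% wider. At an assumed CV of 30% the CI factor goes from ×/÷ 1.360 to ×/÷ 1.385.
- Dose-proportionality slope, half-width t(0.95, n−2)/√Sxx with x = ln dose. For 30 subjects: 1.701/√28.83 = 0.317. For 29, one lost at 640 mg: 1.703/√26.84 = 0.329. Ratio 1.04, so about 4% wider.

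**3. Worst case if the loss depends on exposure.** Assume the highest of the six 640 mg values is the one removed, log-normal data and a true slope of 1. The documents give no CV, so 30, 40 and 50% are assumed. The expected maximum of six standard normal values is 1.267, so removing it shifts the mean of the other five by −1.267/5 = −0.253 SD, with SD = √ln(1 + CV²).

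| CV | SD | Shift in log-mean | Fall in 640 mg GM | ρ^(β−1) |
|---|---|---|---|---|
| 30% | 0.294 | −0.074 | 7% | 0.95 |
| 40% | 0.385 | −0.098 | 9% | 0.93 |
| 50% | 0.472 | −0.120 | 11% | 0.92 |

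For the last column, the change in slope is 5 × (ln 640 − mean x)/Sxx × shift = 5 × 1.434/26.84 × shift = 0.267 × shift, and ρ = 640/40 = 16. At 40%: exp(−0.267 × 0.098 × ln 16) = 0.93. The SAP 10.3.1 limits are 0.80-1.25.

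**The case against.** The strongest reply is that exclusion is not established. Completion of the PK part is undefined. Where the SAP means full sampling it says so, as separate disposition items in 7.1 and Table 9 (all PK blood draws, all PK urine samples, final visit), and none of these is an exclusion criterion. The sentence that sets the condition also accepts subjects with only some parameters estimable, and the exclusion list and Table 10 would keep a withdrawn subject. This stands as far as it goes: the documents do not settle that such a subject is dropped. It does not clear the SAP, because the completion clause is an entry condition and two careful readers would build different Subsets.

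Four stronger readings are tempting but not supported.

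- A reader might infer that every PK output is affected. The listings and the interim analysis are outside the Subset, and 10.2 names no population.
- A reader might infer that AUC0-inf is usually available in those dropped. Under the default rules that holds only for late withdrawal, and the human half-life is not given.
- A reader might take Protocol 5.2.1 as a promise of inclusion in every summary statistic. It says the data are evaluated for PK, and Protocol 10.6 leaves the detail to the SAP. The one-concentration population in Protocol 10.5 matches the SAP's PK Analysis Population, which has no completion condition. The relation is one of tension, not plain breach.
- A reader might take 7-11% as an expected bias. It assumes that the single most exposed subject is the one who leaves. Withdrawal after a single dose cannot reduce exposure, and dosed subjects who discontinue are asked to complete the Day 21 safety assessments. Even then the shifted estimates stay within 0.80-1.25.

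It is also fair that λz-derived parameters already have their own rules. That weakens the case for a completion condition, since those rules protect AUC0-inf, CL/F and Vd/F without it.

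**Conclusion.** The concern holds in limited form. SAP 6.3.2.1 contains an entry condition that, read literally, removes withdrawn subjects with observed Cmax and Tmax from the 10.1 concentration summaries and all 10.3 analyses. After late withdrawal it removes a reportable AUC0-inf as well: after Day 7 at half-lives of 25-33 h, after Day 14 at 64-72 h. The condition contradicts the SAP's own exclusion reasons and sits badly with Protocol 5.2.1.

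The numerical effect of one lost subject is modest: about 4-6% wider intervals if uninformative, and a 7-11% lower 640 mg geometric mean in the worst case. These figures rest on animal half-lives, a one-compartment model, assumed CVs and independent fed and fasted groups. The main reason to act is that inclusion is left open to choice, and the rule can discard valid data selectively, in groups of six.

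**What to change.** In SAP 6.3.2.1, delete the completion clause so that the three listed reasons define the Subset and agree with Table 10. State that each subject enters the analysis of each parameter that can be determined in that dosing period, with the existing λz and %AUCex rules governing AUC0-inf, CL/F and Vd/F. Flag AUC0-last values from profiles cut short by withdrawal while still quantifiable, because they cover a shorter interval than the others. Keep a withdrawn subject's observed concentrations in the nominal-time summaries. Name the population in 10.2.

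The cost is SAP wording and a parameter-level flag in the PK dataset; no data collection or clinical procedure changes. The downside is that N may differ between parameters, so the parameter and comparison tables should show N for each.

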6.4. Covariates and Subgroups

The protocol does not define any formal subgroup analyses.

6.5. Missing Data

All attempts will be made to collect data per protocol. Any missing data or data anomalies will be communicated to the study site for clarification and resolution. Missing collection times for blood and urine PK samples may be imputed as the nominal time if the sample was confirmed to be collected within the protocol defined window. No further imputation of missing data is planned.

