## 6.4 Follow-up

Subjects will return to the CRU within the window indicated for each follow-up timepoint and will undergo procedures as indicated in the Schedule of Study Procedures and Evaluations ([Appendix A](#) VT-1598 Schedule of Study Procedures and Evaluations) and as detailed in [Section 7](#) Description of Clinical and Laboratory Evaluations. Study Procedures/Evaluations: listed below:

### 6.4.1 Day 7 $\pm$ 1

- Review and record any concomitant medications and non-pharmacologic treatments/procedures since Day 4;
- review any change in medical history since Day 4;

- 
- obtain resting vital signs (heart rate, blood pressure, oral temperature and respiration rate, taken after being at rest for at least 5 minutes). If abnormal, these measurements may be repeated once, within 15 minutes of the original assessment;
  - obtain blood sample for PK analysis at 144 ( $\pm 24$ ) hours post-dose;
  - obtain blood samples for fasting (at least 8 hours) clinical chemistry, hematology, and coagulation tests;
  - obtain urine sample for urinalysis;
  - collect and record adverse events (AEs);
  - review post-discharge instructions (including birth control methods, permitted/non-permitted medications, non-medications, dietary and activity restrictions);
  - subjects are released from the CRU after all assessments and procedures are completed and instructed to return for further follow-up evaluation on Day 14.

#### 6.4.2 Day 14 $\pm$ 1

- Review and record any concomitant medications and non-pharmacologic treatments/procedures since Day 7;
- review any change in medical history since Day 7;
- obtain resting vital signs (heart rate, blood pressure, oral temperature and respiration rate, taken after being at rest for at least 5 minutes). If abnormal, these measurements may be repeated once, within 15 minutes of the original assessment;
- obtain blood sample for PK analysis at 312 ( $\pm 24$ ) hours post-dose;
- obtain blood samples for fasting (at least 8 hours) clinical chemistry, hematology, and coagulation tests;
- obtain urine sample for urinalysis;
- collect and record adverse events (AEs);

- review post-discharge instructions (including birth control methods, permitted/non-permitted medications, non-medications, dietary and activity restrictions);
- subjects are released from the CRU after all assessments and procedures are completed and instructed to return for final study visit on Day 21.

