**Table 2: Blood PK Sampling Timepoints**

Blood Sampling Timepoints for VT-1598 and VT-11134 Pharmacokinetic Analyses											
Day 1 (pre-dose)	Cohorts 1-5 (fasting): Taken within 60 minutes prior to dosing										
	Cohort 6 (fed): Taken within 30 minutes prior to start of pre-dose meal.										
Day 1 (hours post dose*)	0.5	1	1.5	2	3	4	6	8	10	12	14
Day 2 (hours post dose**)	24	36									
Day 3 (hours post dose**)	48	60									
Day 4 (hours post dose**)	72										
Day 7 (hours post dose)***	144										
Day 14 (hours post dose)***	312										
Day 21 (hours post dose)***	480										

\*The 0.5-hour post dose blood sample should be taken within  $\pm 5$  minutes of the nominal timepoint. The remaining post dose blood samples on Day 1 should be taken within  $\pm 10$  minutes of the nominal time points.

\*\*The post dose blood samples during the inpatient stay should be taken within  $\pm$  30 minutes of the nominal time point on Days 2, 3 and 4.

\*\*\*For outpatient visits, blood samples should be taken within the visit window.

The exact dates and times of blood collection must be recorded in the eCRF and source documents. The blood samples will be obtained via direct venipuncture or via indwelling intravenous catheter using saline flushes to maintain catheter patency. Specific details for blood sample collection, process blood to plasma, and sample handling are included in the MOP for this study.

Urine samples for the determination of VT-1598 and VT-11134 amounts will be collected in the intervals shown in Table 3:

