If the exact time of plasma PK sample collection is not recorded then the collection time will be imputed as the planned time for analysis, as long as it is not known that the sample was collected outside of the protocol defined window. If the start and/or end time of a urine PK sample is unknown then the missing time(s) will be assumed to be the planned sample collection time (start or end), as long as it is not known that the sample was collected outside of the protocol defined window. If the exact collection time is not known for either sample type, but it is known that the sample was collected outside of the protocol defined time window, then the timepoint may be excluded from analysis at the discretion of the PK analyst. Rationale for excluding results from analysis will be described in the CSR. Results from samples with imputed collection times will be indicated in listings of PK sample concentrations.

All subjects who have at least one quantifiable concentration of VT-1598 or VT-11134 measured will be included in the PK Analysis Population. The bioanalytical laboratory will report VT-1598 and VT-11134 concentrations in plasma and urine in units of ng/mL. Concentrations in plasma and urine will be reported in the same units in the CSR, while cumulative amounts excreted into urine will be reported in units of mg. Drug and metabolite concentrations in plasma and urine will be summarized by Dose Group and listed by subject:

- Subject level concentrations of VT-1598 and VT-11134 in plasma ([Listing 30](#)) and in urine ([Listing 31](#)).
- Subject specific plasma PK parameters for VT-1598 ([Listing 32](#)) and for VT-11134 ([Listing 33](#)).
- Subject specific urine inpatient PK parameters ([Listing 34](#)) and urine nominal collection time interval PK parameters ([Listing 35](#)) for VT-1598 and for VT-11134 ([Listing 36](#) and [Listing 37](#)).

Subject level PK concentration listings will include separate columns for concentrations reported by the lab and concentrations used for analysis. The lab reported concentrations may include codes, such as: "BQL" or "QNS" (Quantity not Sufficient), while the analysis concentrations will contain numeric data only, including imputed values such as 0 for pre-dose timepoints and BQL samples prior to the first quantifiable sample.

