10.2. Noncompartmental Analysis

PK parameters from plasma PK data will be estimated through NCA using version 8.2 or higher of Phoenix WinNonlin®. Actual post dose time will be used for the estimation of plasma PK parameters instead of nominal time. In the case of imputed sample collection times, the imputed time will be included in NCA. PK parameters derived from urine concentration data will be calculated using a combination of Phoenix WinNonlin and SAS version 9.4 or above. Any outliers identified in the PK analysis will be discussed in the analysis report. Outliers will not be excluded from the PK analysis.

Summary statistics of PK parameter estimates by Dose Group will be presented in tables. Summary statistics will include the mean, SD, min, max, CV and GM:

- Plasma PK parameters will be summarized and presented tabularly for all Dose Groups for VT-1598 ([Table 73](#)) and VT-11134 ([Table 80](#)).
- Detailed summary statistics of each plasma PK parameter will be presented tabularly for each Dose Group for VT-1598 (beginning at [Table 74](#) and continuing through [Table 79](#)) and VT-11134 (beginning at [Table 81](#) and continuing through [Table 86](#)).
- Urine PK parameters will be summarized and presented tabularly for all Dose Groups for VT-1598 ([Table 87](#)) and VT-11134 ([Table 94](#)).
- Detailed summary statistics of each urine PK parameter will be presented tabularly for each Dose Group for VT-1598 (beginning at [Table 88](#) and continuing through [Table 93](#)) and VT-11134 (beginning at [Table 95](#) and continuing through [Table 100](#)).

The definition of CV is described below:

For an independent identically distributed random sample $\{x_1, x_2, \dots, x_n\}$ from a log-normal distribution, let s^2 be the sample variance statistic of the natural log-transformed values of the sample. The CV will be defined as:

$$CV = \sqrt{\exp(s^2) - 1}$$

Phoenix WinNonlin NCA will use the following settings to compute parameters from plasma PK data:

- Linear Up Log Down calculation method

- Uniform weighting
- Oral dosing
- Lambda Z Acceptance Criteria
 - $Rsq_{adjusted} \geq 0.90$
 - $Span \geq 3$ half-lives
 - Includes at least 3 timepoints after T_{max}

If an insufficient number of subjects meet the Lambda Z Acceptance Criteria for computing plasma PK parameters, then relaxed Lambda Z Acceptance Criteria may be used and will be described in the CSR.

C_{max}

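### SAP 6.5 and 10.1 conflict on missing PK sampling times, and both let the nominal hour stand in for outpatient samples whose windows are ±24 h or ±48 h

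*SAP*

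**What the plan says.** SAP 6.5 covers blood and urine PK samples. A missing collection time "may be imputed as the nominal time if the sample was confirmed to be collected within the protocol defined window", and the section closes with "No further imputation of missing data is planned".

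SAP 10.1 returns to the same situation. For plasma, the "collection time will be imputed as the planned time for analysis, as long as it is not known that the sample was collected outside" the protocol window. Missing urine start or end times are handled on the same condition. If the sample is known to be out of window, the PK analyst may exclude it.

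SAP 10.2 bases plasma parameters on actual rather than nominal post-dose time, but adds: "In the case of imputed sample collection times, the imputed time will be included in NCA".

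The windows are in the protocol. Day 1 plasma samples have ±5 or ±10 minutes, and Days 2 to 4 have ±30 minutes. After discharge, "For outpatient visits, blood samples should be taken within the visit window": 144 ± 24 h on Day 7, 312 ± 24 h on Day 14 (both section 6.4) and 480 ± 48 h on Day 21 (section 6.5.1).

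**The concern.** There are two separate problems.

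The first is a contradiction. Section 6.5 permits imputation and asks for positive confirmation that the sample was in window. Section 10.1 requires imputation and asks only that nothing shows the sample was out of window. A sample with no time and unknown window status therefore gets no time under 6.5 and the planned time under 10.1. Two analysts following the SAP could build different NCA datasets.

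The second does not depend on which rule wins. For an outpatient sample known to be in window but lacking a clock time, 6.5 allows the nominal hour and 10.1 imposes it. Neither tells the analyst to use the recorded visit date, which may show that the sample was taken one or two days away from nominal. For a drug with a long half-life, the Day 7, 14 and 21 samples carry much of the terminal slope λz, and t1/2, AUC0-inf, CL/F and Vd/F all derive from it. With six active subjects per cohort, one affected subject can move a summary.

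**Working it through.** **The rules side by side, for a sample with no recorded time**

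| Window status | SAP 6.5 | SAP 10.1 |
|---|---|---|
| Confirmed in window | nominal time allowed | planned time required |
| Unknown | no imputation | planned time required |
| Known out of window | no imputation | not imputed; analyst may exclude |

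The rules contradict each other only in the middle row. The nominal hour is available under both in the top row.

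**Inputs for the size of the error.** Sampling times and windows are as above. From SAP 10.2, λz is the uniformly weighted log-linear slope over at least 3 points after Tmax, with adjusted R² ≥ 0.90 and a span of at least 3 half-lives. No human half-life is given. The protocol background gives 25–33 h in rats and 64–72 h in monkeys. The plan states no figure to reproduce.

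**Formula.** Assume a mono-exponential terminal phase without assay noise. Let sample i be taken at tᵢ + d but entered at tᵢ. Regressing ln C on the entered times gives

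λz(est)/λz(true) = 1 + d(tᵢ − t̄)/Sxx,

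and the t1/2 ratio is the reciprocal. The half-life cancels out.

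**Points 144, 312, 480 h.** t̄ = 312 and Sxx = 168² + 0² + 168² = 56,448.

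- Day 21, d = ±48: 48 × 168/56,448 = 0.143. The t1/2 ratio is 1/1.143 = 0.875 (−12.5%) or 1/0.857 = 1.167 (+16.7%). A true 72 h becomes 63 h or 84 h.
- Day 7, d = ±24: 24 × 168/56,448 = 0.071. The change in t1/2 is −6.7% if the sample was really early and +7.7% if late.
- Day 14, d = ±24: tᵢ − t̄ = 0, so the change is 0%.

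**Other point sets**

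- 72, 144, 312, 480 h: t̄ = 252, Sxx = 99,648. For Day 21, 48 × 228/99,648 = 0.110, so t1/2 changes by −9.9% or +12.3%.
- 72, 144, 312 h (480 h below quantification): t̄ = 176, Sxx = 30,336. For Day 14, 24 × 136/30,336 = 0.108, so t1/2 changes by −9.7% or +12.1%. Day 14 is harmless only when it is the central point.
- For comparison, an inpatient error of 0.5 h at 72 h with points 48, 60, 72 h: 0.5 × 12/288 = 0.021, about 2%.

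**Typical rather than extreme error.** If the true Day 21 time is uniform over its window, the λz error x is uniform on ±a with a = 1/7 (three-point set). The mean absolute t1/2 error is −ln(1 − a²)/(2a) = 0.0206/0.2857, about 7%. The mean error is ln[(1 + a)/(1 − a)]/(2a) − 1 = 3.5 × 0.2877 − 1, about +0.7%.

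**Acceptance criteria.** For single in-window errors on the sets above, adjusted R² stayed at 0.975 or higher, so the 0.90 limit would not flag them. The span rule does limit the case: 144 to 480 h is 336 h, so the three-point set qualifies only when the estimated t1/2 is at most 336/3 = 112 h.

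**AUC0-inf.** In a one-compartment profile (ka 0.5/h and t1/2 25–120 h, both assumed), the shift was about 0 to 4.7% for a window-edge error at 480 h and 3.0 to 6.4% at 144 h.

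**With the visit date used.** If only the clock time is missing and the remaining error is at most 12 h (assumed), 12 × 168/56,448 = 0.036 for Day 21, so t1/2 changes by −3.4% to +3.7%.

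**The case against.** A reader might infer that the looser wording in 10.1 causes the window-sized half-life error and that adopting 6.5 would remove it. The documents do not support that. A Day 21 sample at 432 h or 528 h is in window; once that is confirmed, 6.5 also allows 480 h, and the −12.5% or +16.7% is unchanged. What 10.1 adds is samples of unknown status, whose error the window does not cap.

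The conflict itself may also rarely matter for outpatient samples. Their windows run to whole days, so a recorded visit date will usually settle the status. Unknown status is likelier for inpatient samples, where the error is minutes.

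There are safeguards too. Exact dates and times must be recorded, missing data are queried with the site, imputed times are marked in the listings, and the analyst may choose terminal points by hand after viewing the profile. The span rule removes some cases: with a true t1/2 of 100 h, the +16.7% error gives 116.7 h, and the three-point set then fails. Fed–fasted comparisons are exploratory, and the protocol tests no formal hypotheses.

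All of this limits the size and frequency of the problem. It does not decide which rule applies, and flagging an imputed time does not correct it. Nor does it explain why a known visit date should be set aside when SAP 10.2 otherwise insists on actual time. A fair remaining point is that a visit date alone still needs a clock time, so the rule must name one.

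**Conclusion.** The contradiction between SAP 6.5 and 10.1 is real for samples of unknown window status, and it changes what enters NCA. The use of the nominal hour for in-window outpatient samples is a weakness of both rules. Where a time is missing, it can distort λz: at the window edge, t1/2 moves by up to −12.5% or +16.7% for Day 21 on 144, 312 and 480 h, by about 7% for Day 7, and not at all for Day 14 on those points.

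It would go too far to say that half-life will be distorted or biased in one direction. The effect needs a missing time, the average Day 21 error is about +0.7% under the uniform assumption, and the number of missing times, the human half-life and the quantification limit are not in the documents. The percentages assume a mono-exponential, noise-free terminal phase and one mistimed sample per profile. Affected samples should be few. The SAP should still be corrected, because a better rule is available from data already collected.

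**What to change.** State one rule, in the same words, in SAP 6.5 and 10.1, for plasma and urine:

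- Impute the nominal time only when in-window collection is confirmed.
- As an exception for Day 7, 14 and 21 plasma samples with a missing clock time, compute elapsed time from the recorded visit date plus a stated clock time. The vital-sign time from the same visit would serve, since Listing 19 carries it.
- If the date is also unknown, list the sample but leave it out of NCA.

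The cost is a few sentences of SAP text and no new data. Counting the imputed times marked in Listing 30 would show whether any result is affected; if there are none, nothing needs to be rerun.
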